Where, Y_{ijkm} represents the value of the i th family ($i = 1 \dots I$), at the j th time point ($j=1, \dots 3$), in the k th cluster ($k = 1, \dots 200$) and m is the VUP indicator with levels expanded public works, classic public works and mixed. The set of b_{0i} variables represent subject-specific intercepts and are assumed $b_{0i} \sim N(0, \sigma_i)$. The b_{1i} are subject specific slopes and assumed $b_{1i} \sim N(0, \sigma_{slopes})$, the b_{2k} are randomization cluster intercepts and assumed $b_{2k} \sim N(0, \sigma_{region})$ and the b_{3k} are region specific slopes and assumed $b_{3k} \sim N(0, \sigma_{sregion})$. The value e represents residual variation and is assumed $e \sim N(0, \sigma)$. Efficacy will be based on the likelihood ratio test for inclusion of the Time*Treatment interaction (null hypothesis $B_3 = 0$). Random effects will be subject to a limited amount of model building as we would like to simplify the model where appropriate. For example, we would want to test if we can assume a common cluster slope versus a unique slope for each cluster. Cluster and subject-specific effects will be dropped from the model based on a Likelihood Ratio Test (LRT) for their inclusion. The estimation procedure while model building random effects will be Restricted Maximum Likelihood (REML). The primary hypothesis test which is based on the inclusion of a fixed effect will require models estimated by maximum likelihood. Because of randomization we have controlled in theory for all variables observed and unobserved, however treatment group imbalance may still be present. We explore treatment group characteristics for in-balance. However, previous work has showed baseline differences to be minimal.

Model assumptions and alternative tactics: Model assumptions will be verified. In particular we will examine the distributions of the residuals to verify that normality assumptions hold. Residual plots will reveal violations of the normality assumptions. Panel plots will be examined to look at functional shape assumptions within subject. In the case of non-normality of outcomes, we will consider response transformations or the use of models that do not require the normality assumptions including the class of generalized linear mixed effect models. If the linearity

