assumption does not hold across time (baseline, 3 months, and 12 months) we can treat time as a categorical variable to examine differences between the treatment groups at individual time points focusing on the 12-month group differences adjusted for baseline. If examination of panel plots reveals a large amount of heterogeneity among trajectories of the outcomes by subjects we can use Growth Mixture Models which first identify clusters of similar trajectories from which we can test for treatment group differences in terms of membership in the clusters of similar trajectories.

Outliers will be flagged through visual inspection and standardized residual values greater than 3. A sensitivity analysis will be done to determine if outlier removal changes the coefficient values. If we find that outliers are having an oversized effect on the estimated coefficient values we will give preference to the models where the outliers are removed. However, we will present both results.

Some responses are scales or derivations of scales in particular the MDAT and the ASQ. We will examine the psychometric performance of these scales. We are especially concerned with internal consistency and item reliability. If these scales do not show at a minimal amount of internal consistency (Cronbach's Alpha > 0.6) these items will not be considered for analysis. If particular items are an issue they may be dropped from the scale. Research, in areas like Rwanda suffer because standard scales have not been validated on these populations.

Binary Outcome ASQ, shared decision making, father engagement: The analysis for these outcomes will be similar to the analyses above with accommodations being made for the fact the ASQ is a binary outcome. In particular, we will have to make use of mixed effect logistic regression models a form of generalized linear mixed models (GLMM) with a binomial distribution and a logistic link. Outside of accounting for the correct distribution of the response variable the analysis will follow the methods outlined in the previous MDAT section.

Model Assumptions and Alternative Tactics: We will examine Pearson residuals to assess goodness of fit. Alternative methods include the use of quasi-binomial mixed effects regression (in the case of over dispersion). However, such models do not have a full likelihood and instead of LRT test we will have to rely on the Wald-type type test for regression coefficients.

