In fitting logistic mixed effect regression models, it is possible that we may run into numerical difficulties in computing a likelihood ratio test, so score type tests may be needed. This is more likely to occur in the case of testing for variance components.

Count Outcomes, harsh discipline, physical and sexual violence: These metrics count types of harsh discipline action or physical and sexual abuse as suffered or inflicted. Our experience with these scales is that there are more values of zero than what would be predicted by a standard

Poisson distribution. Our analysis will make use of Zero Inflated Poisson (ZIP) models (Everitt, & Hothorn, 2005; Long, 1997). These models belong to the more general class of mixture models. In particular they model the binomial probability of a count of zero versus a count greater than zero and the Poisson probability for counts greater than zero. In particular we will fit mixed effect models as described in the continuous variable sections but under the ZIP distribution assumption.

A key difference between a mixture model and more standard probability distributions is the fixed effects structure and tests for significance can vary between the two parts (binomial and Poisson). Likelihood ratio testing for the Time*Treatment group interaction will be performed for both components of the mixture model. A significant result of the LRT test for the binomial portion would indicate that the probability of no violence (inflicted or suffered) differed between the treatment groups. A significant result of the LRT on the Poisson portion of the ZIP model would indicate that among those who inflicted or suffered harsh discipline or violence the mean amount of violence differed between the treatment groups. The two portions are contained in a single likelihood function and parameter estimation is done simultaneously.

Model Assumptions and Alternative Tactics: The key assumption in these models is the ZIP distribution of the response variables. We will visually inspect the distribution of the outcome variables to verify that we are fitting the correct model. Alternative distributions could be Poisson, Quasi-Poisson, Binomial (data dichotomized due to lack of variability), or Negative Binomial. These are non-mixture models and modeling will follow the process outlined in the continuous outcomes section.

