Secondary Outcomes: Stunting measured by Height-for-Age is an important outcome. However, we do not expect to see significant changes in this variable in the 12-month timespan. We do expect to see a reduction in stunting even if it does not achieve statistical significance. Using the models described in data analysis plan we can extract the coefficient for the time by treatment group interaction as an estimate of the size of the effect of SM on stunting. Effect sizes of other secondary outcomes will be reported similarly.

Missing Data

We will apply the ITT principle to all of our analyses. Unless a subject dies, the ITT convention is to keep them in the study; HLM handles this well since the linearity assumption allows us to estimate subject-specific parameters so long as we have at least two data points. The method of mitigating bias due to missingness known as full-information maximum likelihood estimation (FIMLE) can be problematic in mixed effects linear models. Principled methods of multiple imputation such as chained equations will be employed.

Power and Sample Size

Assuming the linear mixed effect model described above. The following values were used to calculate statistical power. We assumed a total of 200 clusters with 5 families per cluster. We assume a linear relationship over time. The significance level is set at 0.05. The statistical test was the likelihood ratio test for the inclusion of the time by treatment group interaction. The ICC was set at 0.10. A variable for public works type which was categorical with 3 levels was included in the model. Within public works type a ratio 1:1:2 for expanded:both:classic was assumed. Variability was set to one so that effect sizes may interpreted as “Cohen-Like” effect sizes. We found that we have at least 90% power to detect an effect size of 0.25 and at least 80% power to detect an effect size of 0.22. GLIMMSE software was used for these calculations.

E. Safety & Adverse Events

Risks to Subjects

The following risks were identified and submitted to the Boston College IRB:

1. Participation in the intervention may lead adults to confront stressful personal or family issues or generate concern about social harm resulting from loss of confidentiality, which may elicit distress in some participants.
2. In some cases, fatigue from the psychosocial assessment administered pre/post-intervention and at 12-months follow-up may occur.
3. There is a small risk of loss of confidentiality.

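### The Time*Treatment efficacy test can be supplemented or replaced after outcome plots are inspected, with qualitative triggers, no arm-blind requirement and no commitment to report the default test

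*Combined protocol and SAP*

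**What the plan says.** All references are to section D (Data Analysis) of the combined protocol and SAP, unless stated otherwise.

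- **Default test, continuous outcomes.** "Efficacy will be based on the likelihood ratio test for inclusion of the Time*Treatment interaction". Binary outcomes use the logistic mixed-model analogue. Counts use a ZIP mixed model, with the interaction tested in both of its parts.
- **Non-normality.** In that case "we will consider response transformations or the use of models that do not require the normality assumptions".
- **Non-linearity in time.** Time may be made categorical, with the focus moving to baseline-adjusted group differences at 12 months.
- **Heterogeneous trajectories.** "If examination of panel plots reveals a large amount of heterogeneity among trajectories of the outcomes by subjects we can use Growth Mixture Models". The arms are then compared on membership of the trajectory classes. The number of classes and the estimation method are not given.
- **Counts.** The check on the ZIP assumption is by eye: "We will visually inspect the distribution of the outcome variables to verify that we are fitting the correct model". Four fallbacks are then listed without a ranking: "Alternative distributions could be Poisson, Quasi-Poisson, Binomial (data dichotomized due to lack of variability), or Negative Binomial". With ZIP, that makes five distributions.
- **Outliers.** The outlier-removed model is preferred if outliers weigh too heavily on the coefficients, but both sets of results will be shown. No such promise accompanies the other switches.

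Masking is described for enumerators (Randomization Plan; section C, Data Collection). None is described for analysts or for model selection.

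**The concern.** A test holds its level when it is fixed in advance, or chosen by something unrelated to the arm difference. Here the choice depends on judgement of outcome plots, without a threshold, an order of preference or a masking step. An analyst who sees arm results could move, within the plan, towards the more favourable analysis, and the default result need not appear.

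The growth mixture route is the sharpest case. It replaces a difference in slopes with a difference in class membership, where the classes are built from post-randomisation outcomes over three waves. The power calculation covers only the Time*Treatment test. At stake is whether a reported p-value below 0.05 can be read at its nominal level.

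**Working it through.** **1. The plan's own figure.** Inputs from Power and Sample Size: "We assumed a total of 200 clusters with 5 families per cluster", "The ICC was set at 0.10", "The significance level is set at 0.05", and SD 1. Equal allocation and a two-sided test are assumed. This is a single-contrast approximation, because the within-family correlation is not given.

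- Effective n per arm = 500 / (1 + (5 − 1) × 0.10) = 500 / 1.4 = 357.1.
- Standard error = √(2 / 357.1) = 0.0748.
- Effect 0.25: z = 3.34, power 91.6% (stated: at least 90%).
- Effect 0.22: z = 2.94, power 83.6% (stated: at least 80%).

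The stated power is consistent with its inputs. It belongs to the Time*Treatment test and to none of the alternatives.

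**2. Illustrative size if the best of several tests is kept.** For k null test statistics with common correlation ρ, the chance that at least one is significant is

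P = 1 − ∫ φ(u) [Φ((1.96 − √ρ·u)/√(1 − ρ)) − Φ((−1.96 − √ρ·u)/√(1 − ρ))]^k du.

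| k | ρ = 0.7 | ρ = 0.9 |
|---|---|---|
| 2 | 8.3% | 7.0% |
| 3 | 10.9% | 8.4% |
| 4 | 13.0% | 9.4% |

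Both k and ρ are assumptions; the documents give neither.

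**3. Simulation under the null, continuous outcomes.** 200 clusters of 5 families, ICC about 0.10 at baseline, 3,000 runs per scenario (Monte Carlo standard error about 0.4 points). Waves were at 0, 4 and 16 months, as in the Data Analysis Plan; the text on alternative tactics gives 3 and 12 months, and the two should be reconciled. Cluster-mean t-tests stood in for the mixed model, and the variance components were assumed.

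| Analysis | Normal data | Skewed data |
|---|---|---|
| Planned slope test alone | 5.4% | 5.5% |
| Arm-blind choice by rule | 5.3% | 5.0% |
| Best of slope and transformed slope | 5.7% | 7.4% |
| Best of slope and two-class mixture | 7.4% | 9.9% |
| Best of slope, endline, two-class mixture and transformation | 9.2% | 12.7% |

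The first two rows do not differ materially from 5%. The inflation comes from choosing on the result.

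**4. Simulation under the null, counts.** 500 independent families per arm, one time point, scores capped at 7, Wald tests in place of likelihood ratio tests, 6,000 runs per scenario. The count distributions were assumed.

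| Analysis | True ZIP | True negative binomial |
|---|---|---|
| Negative binomial alone | 5.2% | 5.5% |
| Plain Poisson alone | 14.3% | 17.4% |
| Either of the two ZIP tests | 9.1% | 17.0% |
| Any test from the five distributions | 19.4% | 27.2% |

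For counts, masking is not enough: the selected distribution must also fit. Plain Poisson on over-dispersed counts fails even when nobody has seen the arms.

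**The case against.** The strongest defence is that every stated trigger is an ordinary diagnostic: residual distributions, shape over time within subjects, heterogeneity between subjects, and the marginal distribution of counts. None is an arm contrast, and no text says that the plots are split by arm. A reader might infer that the plan lets the arm comparison drive the model, or that the 0.05 level has already been lost. The documents support neither; inflation depends on how the choice is made. That part of the defence stands. What remains is that nothing requires the arm-blind route.

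Three further points limit the concern.

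- **Replacement is permitted, not prescribed.** The Time*Treatment test is called the primary hypothesis test, and the mixture wording is optional. Non-mixture count models are to follow the continuous-outcome process, which points back to the same interaction. But nothing says that the default result will be reported if another analysis is used.
- **Not every switch changes the hypothesis.** Poisson, quasi-Poisson and negative binomial models all target a log rate ratio. In one simulated two-arm sample with fixed effects only, all three gave the coefficient 0.0021, with standard errors of 0.065, 0.086 and 0.088. The hypothesis does change for growth mixture classes, for dichotomised counts and between ZIP and the other count models.
- **Some criticisms of the mixture model go too far.** The plan does not say how classes would be estimated, so one cannot say that classification error is ignored. Normal random slopes cover much heterogeneity, but not distinct trajectory classes.

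Timing is also tempting. The document was finalised on October 8, 2019, and the refresher training before midline collection took place on August 1 to 8, 2018. Midline outcomes may therefore have existed, but the documents do not say whether anyone had examined them by arm. This cannot show data-driven selection.

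**Conclusion.** The concern holds as a pre-specification gap: section D opens a subjective route away from its named test, and for growth mixture models to a different hypothesis, without an arm-blind step or a duty to report the default.

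The size is conditional. If the most favourable of two to four tests is kept, 7% to 13% is a fair illustration under assumed correlations of 0.7 to 0.9. It is not an estimate for this trial: the simulations ran from 5.7% (slope plus transformation, normal data) to 27.2% (all five count distributions, true negative binomial). With an arm-blind rule, continuous outcomes stayed at 5.0% to 5.3%.

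The results do not show that ZIP is the wrong default. The plan justifies it by the team's experience of excess zeros, and putting the negative binomial in its place would be a preference. Two neighbouring matters remain after the change below and need their own rule: the two ZIP tests without a stated alpha split (9.1% when ZIP is true, without any switching), and the outlier preference based on coefficients.

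**What to change.** 1. State that efficacy rests on, and always reports, the prespecified Time*Treatment contrast from the mixed model. For counts, take it from the ZIP default unless the masked rule in step 3 selects another distribution.
2. Label growth mixture models exploratory.
3. Choose any transformation, time coding or count distribution once, by a fixed rule, on data pooled over arms with arm masked. For counts, an example is the lowest AIC among likelihood-based candidates that allow for over-dispersion or excess zeros. That excludes plain Poisson, and also quasi-Poisson, which has no full likelihood. Dichotomising changes the data being modelled, so it needs its own numeric trigger.
4. If categorical time can be selected, name the efficacy contrast in advance.
5. Record the choice before arm codes are merged, and show the other models as sensitivity analyses.

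The cost is SAP wording and one masked run. Design and sample size do not change, and the power check above still applies to the continuous contrast. The downside is small: less analytic freedom after unmasking.

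### For continuous outcomes, the outlier-deleted model is preferred on an undefined degree of influence, without evidence of data error and only after both fits are seen

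*Combined protocol and SAP*

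**What the plan says.** All references are to the combined protocol and SAP, section D (Data Analysis), unless stated.

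- **Efficacy test.** Data Analysis Plan, continuous outcomes: "Efficacy will be based on the likelihood ratio test for inclusion of the Time*Treatment interaction".
- **Flagging.** Model assumptions and alternative tactics, for the same outcomes: "Outliers will be flagged through visual inspection and standardized residual values greater than 3". The coefficients with and without the flagged points are then compared.
- **Preference.** If the analysts find that "outliers are having an oversized effect on the estimated coefficient values we will give preference to the models where the outliers are removed", the deleted fit leads.
- **Reporting.** "However, we will present both results".
- **Related text.** The opening of the Data Analysis Plan provides for range cleaning of the anthropometric data. It also provides for looking at plots to find outliers, with no criterion. Neither step is tied to the preference rule. The Missing Data section commits every analysis to intention to treat. Section C (Data Collection) describes the enumerators as blinded; nothing is said about the analysts.

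**The concern.** The trigger for preferring the deleted model is how far flagged points move the coefficients, not whether those points are wrong. A valid extreme outcome in a randomized child is part of what the trial is meant to estimate. The coefficients are not restricted to nuisance terms, so they include the one that decides efficacy.

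The plan leaves open:

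- how large a shift counts as oversized;
- whether the residual is marginal or conditional, and whether its absolute value is meant;
- whether both flagging criteria must be met or either is enough;
- whether one observation or a whole family is removed;
- whether flagging by eye is blind to arm.

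Because the preference depends on the difference between two fits, it cannot be settled until both are known. At stake is which of two reported estimates leads. Intention to treat is also in tension with preferring a fit that discards observed outcomes, and the plan does not say how the two go together.

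**Working it through.** **1. The plan's own figure.** The plan gives no threshold, expected number of deletions or error rate for the outlier rule, so there is nothing to reproduce for the rule itself. The simulation set-up can be checked against the stated power. Inputs from Power and Sample Size: 200 clusters of 5 families, ICC 0.10, SD 1, alpha 0.05 (two-sided assumed).

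- Design effect = 1 + (5 − 1) × 0.10 = 1.4.
- SE of the difference = √(2 × 1.4 / 500) = 0.0748.
- Power at 0.25: Φ(0.25/0.0748 − 1.96) = Φ(1.38) = 0.916 (plan: at least 90%).
- Power at 0.22: Φ(0.22/0.0748 − 1.96) = Φ(0.98) = 0.836 (plan: at least 80%).

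The single-time approximation agrees with both statements.

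**2. Valid observations that would be flagged.** The Randomization Plan targets at least 1,040 households. Three waves give 1,040 × 3 = 3,120 observations per outcome.

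- Normal residuals: 2 × (1 − Φ(3)) × 3,120 = 8.4.
- Residuals following t with 5 df, scaled to unit variance: 36.6.

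Points would therefore be flagged even with no data error at all.

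**3. Effect on the estimate.** Simulation: 200 × 5, total variance 1, ICC 0.10, difference in means with cluster-robust SE, deletion at |standardized residual| > 3. The deleted fit is used only if |shift|/SE exceeds a trigger. The triggers of 0.25, 0.5 and 1 SE are assumptions, because the plan gives none. There were 8,000 runs per setting.

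| Treated children's response (assumed) | All data | Always deleted | 0.25 SE | 0.5 SE | 1 SE |
|---|---|---|---|---|---|
| 5% gain 2.5 SD | 0.124 | 0.088 | 0.090 | 0.103 | 0.123 |
| 10% gain 2.5 SD | 0.251 | 0.204 | 0.205 | 0.216 | 0.248 |
| 20% gain 1.25 SD | 0.248 | 0.242 | 0.245 | 0.248 | 0.248 |
| All gain 0.25 | unchanged | unchanged | unchanged | unchanged | unchanged |

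The true mean in the first row is 0.05 × 2.5 = 0.125. A repeat with separate code gave 0.125, 0.089 and 0.091 / 0.104 / 0.125 for that row. The relative loss there is (0.124 − 0.090)/0.124 = 27% at 0.25 SE, (0.124 − 0.103)/0.124 = 17% at 0.5 SE, and under 1% at 1 SE. The three triggers fired in 83%, 40% and 0.8% of runs in that row, against 9%, 0.1% and 0% with a homogeneous effect.

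**4. Type I error, same set-up** (Monte Carlo SE about 0.24 points).

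| Residuals | All data | Rule at 0.25 / 0.5 / 1 SE | Always deleted |
|---|---|---|---|
| Normal | 5.1% | 5.4 / 5.1 / 5.1% | 5.8% |
| t, 5 df | 5.0% | 5.2 / 4.9 / 5.0% | 6.1% |

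**5. What an all-data primary fit costs.** Same design, effect 0.22:

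- 1% gross errors with SD 6 (assumed): power about 73% with all data and 83% if flagged points are always deleted. A companion run (74% with all data) gave 81 / 78 / 75% under the three triggers.
- Valid t residuals with 5 df: 83% with all data, 87% always deleted.

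**The case against.** The best defence has three parts.

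- **Both fits are promised without condition**, so no reader is denied the all-data estimate. This stands, and it confines the harm to the choice of headline.
- **Harm to the estimate needs a small group of strong responders.** Nothing in the documents predicts one, and a shift of 0.25 SE is hardly oversized on an ordinary reading. This also stands: at 1 SE, or with a diffuse effect, the rule does almost nothing.
- **Deletion protects against gross errors.** Range cleaning is planned only for anthropometrics, so an all-data fit of MDAT scores could lose power. This stands too and has to be counted as a cost. It argues for error checks on every continuous outcome, not for using influence on the coefficients as a stand-in for error.

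A reader might infer more in three directions that the documents do not support.

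- *That the rule lets the sponsor report whichever fit is significant.* It does not. The preference runs one way, towards deletion, regardless of the sign of the shift or the p-value. In the responder scenarios deletion understates the intervention.
- *That the rule also deletes events in the binary outcomes*, because there "the analysis will follow the methods outlined in the previous MDAT section". The outlier rule sits in the continuous-outcome part. The binary part has its own assumptions paragraph, where the stated use of residuals is diagnostic: "We will examine Pearson residuals to assess goodness of fit". Carrying the deletion rule over is conjecture.
- *That the other alternatives in the same paragraphs, such as* "we will consider response transformations or the use of models that do not require the normality assumptions" *or* "we can use Growth Mixture Models which first identify clusters of similar trajectories"*, compound the preference rule.* They are worded as options and do not alter it.

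**Conclusion.** The point holds for the continuous outcomes. The plan prefers a deleted fit on an undefined degree of influence, asks for no evidence of error, and leaves the preference to be settled after both estimates are known. This should be changed, but it does not threaten the trial's validity.

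Under a homogeneous effect the estimate is unbiased, and type I error under the rule stays near 5%. If 5% of treated children gain 2.5 SD, the preferred single-time estimate drops from about 0.125 to 0.09-0.10 at triggers of 0.25-0.5 SE and barely moves at 1 SE.

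These sizes rest on the assumed responder group, the assumed triggers, absolute residuals, and a single-time comparison in place of the planned three-wave mixed model. The textual finding rests on none of them.

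**What to change.** 1. Name the all-data intention-to-treat fit as primary for every continuous outcome.
2. Remove or correct only values shown to be errors or lying outside pre-stated biological or instrument limits. Decide this blind to arm, and extend it beyond anthropometrics to the other continuous outcomes.
3. Report the outlier-deleted fit, or a robust fit, as a sensitivity analysis. State in advance the residual type, the absolute cut-off and the unit removed.

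This is a change of SAP wording. Both fits are already promised, and the sample-size calculation is untouched. The cost is some power if gross errors get past the range checks or residuals are heavy-tailed: at effect 0.22, illustratively 73% instead of 83%, and 83% instead of 87%, when compared with always deleting.
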